2.7.4 Supportive analyses

Not applicable.

2.8 Safety analyses

All the safety analysis will be performed on Safety Set.

Summaries may performed separately for initial (Weeks 1-16) and entire Treatment Period till Week 52.

The analyses for treatment-emergent adverse events, serious adverse events and risks based on adverse events will be summarized. Safety analyses will be performed on treatment received or actual treatment as described below:

The actual treatment or treatment received for summaries of safety data will differ from the treatment assigned at randomization only if a subject received the wrong treatment during the entire study.

For those patients who received not the treatment randomized, i.e. who received erroneously the wrong treatment at least once, an additional AE listing will be prepared displaying which events occurred after the treatment errors.

2.8.1 Adverse events (AEs)

The crude incidence of treatment emergent adverse events (i.e. events started after the first dose of study treatment or events present prior to the first dose of study treatment but increased in severity based on preferred term) will be summarized by primary system organ class and preferred term. Confidence intervals for the crude rate will be reported, using the statistical methods described in Section 5.4.5.

In addition, exposure time-adjusted rates (incidence rate) including 95% confidence intervals will be provided for Treatment Period 1 and Treatment Period 2 to adjust for differences in

exposure. The description of exposure calculation is mentioned in Section 2.4.1. The statistical methods for calculation of exposure-adjusted incidence rate and its 95% confidence interval are described in Section 5.4.4. A graphical display of the crude incidence rates and exposure-adjusted rates will be presented for all AEs and serious AEs by system organ class.

Adverse events will be summarized by presenting, for each treatment group, the number and percentage of patients having at least one AE, having an AE in each primary system organ class and having each individual AE (preferred term). Summaries (crude incidences only) will also be presented for AEs by severity and for study treatment related AEs. If a particular AE 'severity' is missing, this variable will be listed as missing and treated as missing in summaries. If a subject reported more than one adverse event with the same preferred term, the adverse event with the greatest severity will be presented. If a subject reported more than one adverse event within the same primary system organ class, the subject will be counted only once with the greatest severity at the system organ class level, where applicable.

Separate summaries will be provided for

- adverse events suspected to be related to study drug by the investigator
- deaths
- serious adverse events
- adverse events leading to discontinuation
- adverse events leading to temporary dose interruption
- non-serious adverse events

Adverse events will also be reported separately by SMQ according to MedDRA, using a narrow search. The MedDRA version used for reporting the study will be described in a footnote.

A listing of non-treatment emergent adverse events will be done. These adverse events occurred before the first dose of the study treatment. The crude incidence rate will be provided without treatment information.

Algorithms for date imputations will be provided in Programming Specifications.

For SAEs occurred during screening a listing will be prepared for all patients screened including screening failures.

An overview of the safety analyses and which will be performed for each analysis period is described in Table 2.1 below.

Table 2.8-1 Overview of analyses on some safety data

Analysis period	AEs & SAEs	AEs by severity	Study drug related AEs	AEs-SMQ	Risk	Notables for (vitals/ECG), lab criteria
--------------------	---------------	--------------------	------------------------------	---------	------	---

Day 1 – Week 16	• Crude Incidenc e	• Crude Incidence	• Crude Incidence	• Crude Incidence	• Crude Incidence	• Crude Incidence
	• Exposure time adjusted incidence					
Entire Treatment (upto Week 52)	 Crude Incidenc e Exposure time adjusted incidence * 	• Crude Incidence	• Crude Incidence	• Exposure time adjusted incidence *	 Crude Incidence Exposure time adjusted incidence * 	• Crude Incidence

*Exposure-adjusted incidence rates will be done for the following:

• at the PSOC for AE and SAE

• at the PT level for common AEs, which is defined as at least 2% of the patients in the combined secukinumab groups during the initial Treatment Period or events that had an incidence rate of at least 5.0 cases per 100 subject-years in the combined secukinumab groups during the entire treatment period

• at Level 1 for Risks and SMQ analyses

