2.1 Data analysis general information

Data will be analyzed by Novartis Product Life-Cycle Services and/or a designated Contract Research Organization.

It is planned that the data from all centers that participate in this protocol will be combined, so that an adequate number of patients will be available for analysis. Analysis datasets and statistical outputs will be produced using the most recent SAS[®] Version 9.4 (SAS Institute Inc., Cary, NC, USA), and stored in Novartis global programming & statistical environment (GPS).

As the primary analysis time point is Week 16, there will be a database lock after all patients have completed the Week 16 visit and data are clean and complete. At that time, only the statistician and programmer(s) from Novartis and/or a designated CRO will be unblinded in order to perform the analysis. Results from the analyses of all data through Week 16 will be shared internally. For publication purposes, summary results from the Week 16 primary analysis time point may be shared with the health care community; however, individual subject-level data will remain blinded until the end of the trial. A final database lock will occur when all patients have completed the study.

Summary statistics for continuous variables will include mean, standard deviation, standard error of mean, median, 25th and 75th percentiles, interquartile range, minimum, and maximum at each time point. Summary statistics for discrete variables will be presented in the number and percent of patients in each category. Summary statistics will also be presented graphically wherever applicable. If not otherwise specified, p-values and confidence interval (CI) will be presented as two-sided and the default level of significance will be set to 0.05 (two-sided). For all continuous variables (efficacy and safety), change from baseline and percentage change from baseline by visit will also be presented.

Data analyses will be presented by treatment group. Efficacy and safety data for the placebocontrolled period (or the entire Treatment Period as appropriate) will be presented by the following 3 treatment groups. Patients may be included in more than one treatment group for some analyses (e.g. exposure-adjusted adverse events over the entire treatment period).

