2.4 Treatments (study treatment, rescue medication, concomitant therapies, compliance)

2.4.1 Study treatment / compliance

Study Treatment

The summaries by treatment group will be performed cumulatively by the actual treatment received (as follows) for every visit until Week 16.

Treatment groups in Treatment Period 1:

- Secukinumab 300 mg
- Secukinumab 150 mg
- Placebo

For entire treatment period, the summaries by treatment group will be performed cumulatively by the actual treatment received (as follows) for every visits till Week 52, including the patients who switched at Weeks 16, 28, 40.

Treatment groups for entire treatment period analysis:

For efficacy variables:

- Secukinumab 300 mg
- Secukinumab 150 mg 150 mg (R)
- Secukinumab 150 mg 300 mg (NR)
- Any Secukinumab 150 mg
- Placebo Secukinumab 300 mg

For safety variables

- Any Secukinumab 150 mg
- Any Secukinumab 300 mg
- Any Secukinumab

The analysis of study treatment data will be based on the Safety Set. The number of active and placebo injections will be summarized by treatment group up to Week 52.

Duration of exposure

The duration of exposure to study treatment will also be summarized by treatment group. In addition, the number and percentage of subjects with cumulative exposure levels (e.g. any exposure, ≥ 1 weeks, ≥ 2 weeks, ≥ 3 weeks, ≥ 4 weeks, ≥ 8 weeks, etc.) will be presented.

Duration of exposure of study Treatment Period 1 will be defined as the time from first dose of study treatment till the end of Treatment Period 1 (Week 16).

Duration of exposure of switched treatment group (for patients switching from placebo to secukinumab 300 mg, or secukinumab 150 mg to 300 mg) in Treatment Period 2 will be defined as the time from treatment switch to end of Treatment Period 2 (Week 52).

The duration of exposure of initial treatment group in Treatment Period 2 will be defined as the time from first dose (Week 16) till the end of Treatment Period 2 (for secukinumab 300 mg group) or until the switch (for secukinumab 150 mg group).

For patients who discontinue, this will be the patient's last visit in the corresponding treatment period.

Duration of exposure (years) = duration of exposure (days) / 365.25

Duration of exposure (100 patient years) = duration of exposure (years) / 100

The analyses of duration of exposure described above will be done for the entire study treatment periods.

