2.14 Interim analysis

The database of this study will be locked twice, first after the end of Treatment Period 1 (Week 16) and again after the end of Treatment Period 2 (Week 52). Data analyses will follow after database lock at Week 16. The main analysis for the primary objective will be done at Week 16. As Week 16 is the primary analysis time point, no adjustment to the significance level of 0.05 will be made.

3 Sample size calculation

The sample size was calculated based on the primary efficacy variable (i.e., ACR20 response) for the primary comparison (i.e., secukinumab 300 mg versus placebo). ACR20 response rates of 50% for secukinumab 300 mg and 20% for placebo (corresponding to an Odds ratio of 4) at Week 16 were assumed, based on results from AIN457F2312 (FUTURE 2) study. Using a continuity-corrected chi-squared test, an allocation ratio of 2:1, a two-sided significance level of 0.05, and a power of 0.90, approximately 88 patients in secukinumab 300 mg group and 44 patients in placebo group will be needed.

Assuming a loss to follow-up rate of 10% and a 2:2:1 allocation ratio (secukinumab 300 mg: secukinumab 150 mg: placebo), the total number of randomized patients will be approximately 250 (100 on secukinumab 300 mg, 100 on secukinumab 150 mg, and 50 on placebo).

The sample size estimation was done using query Advisor 7.0.

4 Change to protocol specified analyses

Not applicable.

5 Appendix

This section will be used later for drafting CSR Appendix 16.1.9.

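### Over 52 weeks, AEs by severity, study-drug-related AEs and notable laboratory and vital-sign values are reported as crude percentages only, in dose groups whose follow-up per patient differs by design.

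*SAP*

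**What the plan says.** For AEs by severity and related AEs, SAP 2.8.1 says: "Summaries (crude incidences only) will also be presented for AEs by severity and for study treatment related AEs". In Table 2.8-1, the row headed "Entire Treatment (upto Week 52") lists crude incidence alone for AEs by severity, study-drug-related AEs and notable values. In the same row, AEs and SAEs, SMQs and Risks have exposure-adjusted incidence. The table's footnote sets the level for those rates: "at the PSOC for AE and SAE", preferred terms for common AEs, and Level 1 for Risks and SMQs.

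SAP 2.8.1 gives its reason for these rates, which "will be provided for Treatment Period 1 and Treatment Period 2 to adjust for differences in" exposure.

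SAP 2.4.1 defines the groups: "For entire treatment period, the summaries by treatment group will be performed cumulatively by the actual treatment received (as follows"). For safety these are "Any Secukinumab 150 mg", Any 300 mg and Any secukinumab. SAP 2.1 adds: "Patients may be included in more than one treatment group for some analyses"; its one example is an exposure-adjusted AE analysis.

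Under SAP 1.1, 150 mg patients who fail the joint-count responder rule at Week 16, 28 or 40 move to 300 mg, and all placebo patients move to 300 mg at Week 16.

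**The concern.** A crude percentage treats each patient as one unit, however long that patient was at risk. A 150 mg patient who switches at Week 16 has 16 weeks in which to contribute a 150 mg event, against 52 weeks for one who never switches. On 300 mg, former placebo patients contribute 36 weeks, and switchers 36, 24 or 12 weeks. A side-by-side reading of the 52-week columns therefore mixes risk with observation time. The SAP recognises this and corrects for it in most AE displays, but no planned table corrects it for these three. A reader could take a difference in severe or related AEs for a dose effect when it reflects follow-up, or miss a real one.

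**Working it through.** **Inputs from the documents**
- Group sizes: "100 on secukinumab 300 mg, 100 on secukinumab 150 mg, and 50 on placebo" (SAP Section 3).
- Time on 150 mg: 16, 28 or 40 weeks if switched, 52 if not. Time on 300 mg: 52 weeks if randomized to it, 36 for placebo patients, and 36, 24 or 12 for switchers (SAP 1.1). SAP 2.4.1 ends 150 mg exposure at the switch and runs switched exposure to Week 52.

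**The plan's own figure.** The group sizes reproduce. For 50% against 20%, 2:1 allocation, two-sided 0.05, 90% power and continuity correction, I obtain 88 and 44. Then 88/0.9 = 97.8 and 44/0.9 = 48.9, or 98 and 49, which round to 100 and 50.

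**Assumptions.** The documents give no switch rate, so I vary it: s16, s28 and s40 are the shares of the 150 mg arm switching at Weeks 16, 28 and 40. I assume no dropout, a constant event rate that is the same on both doses, and, at first, that Any 150 mg counts only time on 150 mg.

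**Formulas**
- Mean weeks, Any 150 mg = 16·s16 + 28·s28 + 40·s40 + 52·(1 − s16 − s28 − s40).
- Mean weeks, Any 300 mg = (100·52 + 50·36 + 36·n16 + 24·n28 + 12·n40) / (150 + n16 + n28 + n40), where n = 100·s.
- Crude incidence = group mean of 1 − exp(−λt), with λ = −ln(0.95)/52 per week, which is a 52-week risk of 5%.

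**Example, 50/10/5%**
- Any 150 mg: 8 + 2.8 + 2 + 18.2 = 31.0 weeks.
- Any 300 mg: (5200 + 1800 + 1800 + 240 + 60)/215 = 9100/215 = 42.3 weeks.
- Ratio: 0.73.

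| Switching at Weeks 16/28/40 | Any 150 mg, weeks | Any 300 mg, weeks | Ratio | Crude 150 vs 300 | 150 relative to 300 |
|---|---|---|---|---|---|
| 0/0/0% | 52.0 | 46.7 | 1.11 | 5.00% vs 4.50% | +11% |
| 10/0/0% | 48.4 | 46.0 | 1.05 | 4.66% vs 4.43% | +5% |
| 20/0/0% | 44.8 | 45.4 | 0.99 | 4.31% vs 4.38% | −1.5% |
| 30/0/0% | 41.2 | 44.9 | 0.92 | 3.97% vs 4.33% | −8% |
| 30/5/5% | 39.4 | 43.5 | 0.91 | 3.80% vs 4.19% | −9% |
| 40/10/5% | 34.6 | 42.6 | 0.81 | 3.34% vs 4.11% | −19% |
| 50/10/5% | 31.0 | 42.3 | 0.73 | 3.00% vs 4.08% | −27% |

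**Break-even.** With switching at Week 16 only, the means are equal when (52 − 36s)(150 + 100s) = 7000 + 3600s. This reduces to 36s² + 38s − 8 = 0, so s = 0.18.

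**Where the truth may lie.** Protocol 3.3 reports 51.0% ACR20 on 150 mg at Week 24 in CAIN457F2312, so about 49% non-response. The switch rule uses the two joint counts only and is easier to meet than ACR20, so 50% switching at Week 16 is near a ceiling.

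**Sensitivity.** Exponential dropout of 10% over 52 weeks leaves the ratio at 0.91 for 30/5/5% and moves it from 0.73 to 0.74 for 50/10/5%. At a 52-week risk of 60%, the extremes narrow to +8% and −23%.

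**Other reading of Any 150 mg.** If up-titrated patients stay in Any 150 mg to Week 52, its mean is 52.0 weeks. If they also enter Any 300 mg from the switch, the ratio is 52.0/46.7 = 1.11 with no switching and 52.0/42.3 = 1.23 at 50/10/5%.

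**After the fix.** Events divided by time at risk (SAP 5.4.4) give about 5.1 per 100 patient-years on both doses in every row of the table, a ratio of 1.00.

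**The case against.** A reader might infer that the crude tables will make 150 mg look 10–27% safer. The documents do not support that. It needs roughly 30–50% of the arm to switch at Week 16 with more later, and below about 18% at Week 16 alone the distortion runs the other way.

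It also needs Any 150 mg to mean time on 150 mg only, which the SAP leaves open. SAP 2.8 says that actual treatment departs from randomized treatment only if the wrong treatment was received throughout. In the efficacy list of SAP 2.4.1, the same label stands beside the 150–150 and 150–300 subgroups, which suggests the whole randomized arm. The SAP 2.1 sentence on multiple membership is illustrated only by an exposure-adjusted analysis. These points stand. They leave follow-up unequal under either reading, and they add a need to define the groups.

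Nor are these displays the main basis for comparing doses. The safety objective compares each dose with placebo, and Protocol 9.5.2 only calls for severity and relatedness to be listed as appropriate. The main AE displays are exposure-adjusted, exposure is tabulated by group, and the three displays also have Day 1 to Week 16 tables with equal planned follow-up. This limits the importance of the point. ECG is not part of it: Protocol Table 6-1 schedules ECG at screening only, and SAP 2.8.4.1 only lists the data.

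**Conclusion.** The point holds as an inconsistency in the SAP: three entire-period displays are crude only, while groups with unequal time on dose receive exposure-adjusted rates elsewhere for that very reason. At equal true risk, and with Any 150 mg counting only time on 150 mg, the 150 mg percentage lies between about 11% above and 27% below the 300 mg percentage in relative terms. The direction is set by a switch rate that the documents do not state. If up-titrated patients remain in Any 150 mg, its follow-up is instead about 11–23% longer than that of Any 300 mg. All figures assume the planned group sizes, a constant rate and, except where varied above, no dropout. The efficacy analyses and the Day 1 to Week 16 safety comparison are unaffected. The correction is cheap and worth making.

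**What to change.** In SAP 2.8.1 and Table 2.8-1, add entire-period exposure-adjusted incidence rates, with the SAP 5.4.4 interval, for severe AEs, study-drug-related AEs and newly notable laboratory and vital-sign values, by Any 150 mg, Any 300 mg and Any secukinumab. State in SAP 2.4.1 that Any 150 mg and Any 300 mg count events and time while on that dose, and reconcile this with the actual-treatment sentence in SAP 2.8. State that crude percentages are compared between groups only for Day 1 to Week 16.

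The cost is a few more tables from an existing method and no new data. Two limits should be noted beside the tables. The rate assumes constant intensity, which is rough for laboratory values seen only at spaced visits. It also does not remove the selection of 150 mg non-responders into the 300 mg group.

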2.8.1.1 Adverse events of special interest / grouping of AEs

Adverse events of special will be summarized by presenting, for each treatment group, the number and percentage of patients having at least one AE, having an AE in each primary system organ class and having each individual AE (preferred term).

2.8.2 Deaths

Separate summaries and listings will be provided for deaths for each treatment period.

2.8.3 Laboratory data

The summary of laboratory evaluations will be presented for three groups of laboratory tests (hematology, chemistry and urinalysis).

For urinalysis, frequency tables will be presented.

Descriptive summary statistics for the change from baseline to each study visit will be presented. These descriptive summaries will be presented by laboratory variable and treatment group. Change from baseline will only be summarized for patients with both baseline and

post-baseline values and will be calculated as:

change from baseline = post-baseline value – baseline value

For each variable, the maximum change (maximum decrease and maximum increase) from baseline within each study period will be analyzed analogously.

QuantiFERON TB-Gold test will also be analyzed by the central laboratory.

In addition, shift tables will be provided for all variables to compare a patient's baseline laboratory evaluation relative to the visit's observed value. For the shift tables, the reference laboratory ranges will be used to evaluate whether a particular laboratory test value was normal, low, or high for each visit value relative to whether or not the baseline value was normal, low, or high. Also the shifts to the most extreme laboratory test value within a Treatment Period will be presented as well (including category "high and low"). These summaries will be presented by laboratory test and treatment group.

The following laboratory variables will be analyzed with respect to numerical Common Terminology Criteria for Adverse Events (CTCAE) grades, given in Table 2.8-2: hemoglobin, platelets, white blood cell count, neutrophils, lymphocytes, creatinine, total bilirubin (TBL), gamma-glutamyl transferase (GGT), alanine aminotransferase (ALT), aspartate aminotransferase (AST), alkaline phosphatase (ALP), glucose, cholesterol, triglycerides (TG).

CTCAE Term	Grade 1	Grade 2	Grade 3	Grade 4
HGB decreased (Anemia)	<lln -="" 100="" g="" l<="" td=""><100 - 80 g/L	<80 g/L		</lln>	<100 - 80 g/L	<80 g/L	
Platelet count Decreased	<lln 75.0="" x10e9
/L</lln>	<75.0 - 50.0 x10e9 /L	<50.0 – 25.0 x10e9 /L	<25.0 x 10e9 /L
White blood cell Decreased	<lln -="" 10e9="" 3.0="" l<="" td="" x=""><3.0 - 2.0 x 10e9 /L	<2.0 - 1.0 x 10e9 /L	<1.0 x 10e9 /L	</lln>	<3.0 - 2.0 x 10e9 /L	<2.0 - 1.0 x 10e9 /L	<1.0 x 10e9 /L
Decreased Lymphocyte	<lln -="" 1.5="" 10e9="" l<="" td="" x=""><1.5 - 1.0 x 10e9 /L	<1.0 - 0.5 x 10e9 /L	<0.5 x 10e9 /L	</lln>	<1.5 - 1.0 x 10e9 /L	<1.0 - 0.5 x 10e9 /L	<0.5 x 10e9 /L
count Decreased	<lln -="" 0.8="" 10e9="" l<="" td="" x=""><0.8 - 0.5 x 10e9 /L	<0.5 - 0.2 x 10e9 /L	<0.2 x 10e9 /L	</lln>	<0.8 - 0.5 x 10e9 /L	<0.5 - 0.2 x 10e9 /L	<0.2 x 10e9 /L
Creatinine increased*	>1 - 1.5 x baseline; >ULN - 1.5 x ULN	>1.5 - 3.0 x baseline; >1.5 - 3.0 xULN	>3.0 baseline; >3.0 - 6.0 x ULN	>6.0 x ULN
TBL increased	>ULN - 1.5 x ULN	>1.5 - 3.0 x ULN	>3.0 - 10.0 x ULN	>10.0 x ULN
GGT increased	>ULN - 2.5 x ULN	>2.5 - 5.0 x ULN	>5.0 - 20.0 x ULN	>20.0 x ULN
ALT increased	>ULN - 3.0 x ULN	>3.0 - 5.0 x ULN	>5.0 - 20.0 x ULN	>20.0 x ULN
AST increased	>ULN - 3.0 x ULN	>3.0 - 5.0 x ULN	>5.0 - 20.0 x ULN	>20.0 x ULN
ALP increased	>ULN - 2.5 x ULN	>2.5 - 5.0 x ULN	>5.0 - 20.0 x ULN	>20.0 x ULN

Table 2.8-2CTCAE grades for laboratory variables to be analyzed

Glucose increased				
(Hyperglycemia				
)	>ULN - 8.9 mmol/L	>8.9 - 13.9 mmol/L	>13.9 - 27.8 mmol/L	>27.8 mmol/L
Glucose				
decreased				
(Hypoglycemia)	<lln -="" 3.0="" l<="" mmol="" td=""><3.0 - 2.2 mmol/L	<2.2 - 1.7 mmol/L	<1.7 mmol/L	</lln>	<3.0 - 2.2 mmol/L	<2.2 - 1.7 mmol/L	<1.7 mmol/L
		>7.75 - 10.34		
Cholesterol high	>ULN - 7.75 mmol/L	mmol/L	>10.34 - 12.92 mmol/L	>12.92 mmol/L
Hypertriglycerid				
emia	1.71 - 3.42 mmol/L	>3.42 - 5.7mmol/L	>5.7 - 11.4 mmol/L	>11.4 mmol/L
*NT-4 C		1	1	

*Note: for "creatinine increased" the baseline criteria do not apply

Shift tables will be presented comparing baseline laboratory result (CTCAE grade) with the worst results (expressed in CTCAE grade) during the treatment phase (either initial or entire) analyzed. Of note, baseline will be defined as last assessment prior to first dosing in initial treatment phase. Patients with abnormal laboratory values will be listed and values outside the normal ranges will be flagged.

Newly occurring or worsening liver enzyme abnormalities will also be summarized based on the event criteria given in Table 2.8-3 below:

Parameter	Criterion
ALT	>3xULN; >5xULN; >8xULN;>10xULN, >20xULN
AST	>3xULN; >5xULN; >8xULN >10xULN; >20xULN
ALT or AST	>3xULN; >5xULN; >8xULN >10xULN; >20xULN
TBL	>1.5xULN, >2xULN, >3xULN,
ALP	>2xULN, >3xULN. >5xULN
ALT or AST &	ALT or AST>3xULN & TBL >2xULN;
TBL	ALT or AST >5xULN & TBL >2xULN;
	ALT or AST >8xULN & TBL >2xULN;
	ALT or AST >10xULN & TBL >2xULN
ALP & TBL	ALP >3xULN & TBL >2xULN
	ALP >5xULN & TBL >2Xuln
ALT or AST &	ALT or AST>3xULN & TBL >2xULN & ALP <2xULN (Hy's Law)
TBL & ALP	Note: elevated ALP may suggest obstruction as a consequence of gall
	bladder or bile duct disease; ALP may also be increased in
	malignancy. FDA therefore terms Hy's Law cases as indicators of
	pure hepatocellular injury. This does not mean that cases of ALT or
	AST >3xULN & TBL >2xULN & ALP ≥2xULN may not result
	in severe DILI.

Table 2.8-3Liver-related events

Notes:

In studies which enroll patients with pre-existing liver disease, baseline LFT may be increased above ULN; in such a case it is meaningful to add the condition "and worse than baseline" to the abnormality Criteria

For a combined criterion to be fulfilled, all conditions have to be fulfilled on the same visit. The criteria are not mutually exclusive, e.g. a subject with ALT = 6.42xULN is counted for ALT > 3xULN and ALT > 5x ULN.

Novartis	For business use only	Page 34
SAP		Secukinumab/AIN457FUS01

Individual subject data listings will be provided for patients with abnormal laboratory data. Data of patients with newly occurring or worsening liver enzyme abnormalities will be listed in an additional listing.

Separate summaries and listings will be provided for urine pregnancy results by visit for each treatment period.

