 - Patients who did not meet the responder criteria at Week 16, 28 or 40 will start receiving secukinumab 300 mg every 4 weeks and will continue this dose up to Week 48.
- Patients on placebo (**Group 3**) regardless of their responder status will start receiving secukinumab 300 mg every 4 weeks from Week 16 up to Week 48.

Those patients whose tender and swollen joint counts both reduce by $\ge 20\%$ from baseline will be classified as 'responders' and those patients who do not meet the responder criteria will be classified as 'nonresponders'.

Patients, investigators/site staff, persons performing assessments, and Novartis study personnel will remain blinded to individual treatment assignment from the time of randomization until the final database lock.

Rescue medication will not be allowed during the day of the clinical visit and before

completion of Week 16 assessments. Although no subject will be restricted from receiving necessary rescue medications for lack of benefit or worsening of disease, patients will be discontinued from the study if rescued with prohibited biologics and should obtain end of study assessments at the earliest possible date, provided consent to do so has not been withdrawn.

No stratification at randomization will be performed.

The following figure describes the study design.

Figure 1.1: Study Design

Primary analysis time point

The primary analysis will be performed at Week 16.

Interim analyses

As planned, database lock will be performed at the end of Treatment Period 1 (Week 16), after all patients have completed the Week 16 visit. Data analyses will follow after first database lock.

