2.1.1 General definitions

Study treatment

• Investigational Treatment:

Secukinumab **150 mg** provided in 1.0 mL in PFS for s.c. injection.

Secukinumab **placebo** provided in 1.0 mL in PFS for s.c. injection.

Dates and time windows

Study treatment start and end date

Study treatment start date is defined as the first date when a non-zero dose of study drug is administered and recorded on the Drug Administration Record (DAR) CRF page. Similarly, **study treatment end date** is defined as the last date when a non-zero dose of study drug is administered and recorded on the DAR CRF page of the core study.

Study day

Study day will be calculated as (event date – study drug start date + 1 day) for events that occurred on or after study drug start date (e.g., visit, lab samples, AEs). For events prior to study drug start date (e.g., time of diagnosis), study day will be negative and calculated as (event date – study drug start date). Note that study drug start date is study day 1 and the day before study drug start date is study day -1 (i.e. no study day 0).

Due to the study drug dosing schedule, one month will be considered as 28 days. However, for "time since event" data (e.g., medical history), one month will be considered as 365.25/12 days for events that occurred prior to study Day 1. Time from events prior to the start of study drug, e.g., time since diagnosis, is calculated as the difference between the start date of study drug and the date of prior event.

Note that, the first dose day is Day 1, and the day before the first dose day is counted as Day - 1 (not Day 0).

Baseline and post-baseline definitions

In general, a baseline value refers to the last measurement made prior to administration of the first dose of study treatment. A post-baseline value refers to a measurement taken after the first dose of study treatment.

Treatment Period: There are 2 Treatment Periods for this study defined as:

Treatment Period 1 is defined as the 16-week, placebo-controlled, double-blind Treatment Period starting from baseline till Week 16.

Treatment Period 2 is a 36-week, double-blind active Treatment Period starting from Week 16 till Week 52.

Lost to follow up: The patients whose study completion status is unclear because they fail to appear for study visits without stating an intention to withdraw

On-treatment period: The period where the patients are exposed to the study treatment. For this study the treatment phase consists of 52 weeks.

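### The entire-period CTCAE shift tables keep a pre-placebo baseline after the Week 16 switch, so abnormalities that began on placebo and persist are scored as shifts on secukinumab 300 mg

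*SAP*

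**What the plan says.** **Baseline.** SAP 2.1.1 gives the general rule that "a baseline value refers to the last measurement made prior to administration of the first dose of study treatment". SAP 2.8.3 repeats it for the CTCAE-graded tables: "Of note, baseline will be defined as last assessment prior to first dosing in initial treatment phase". For a placebo patient, the first study dose is a placebo dose.

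**Post-baseline value.** The same paragraph of SAP 2.8.3 compares that baseline "with the worst results (expressed in CTCAE grade) during the treatment phase (either initial or entire) analyzed". The single baseline therefore applies to the 52-week table as well as the 16-week one.

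**Switch.** Under SAP 1.1, Group 3 patients, responders or not, "will start receiving secukinumab 300 mg every 4 weeks from Week 16 up to Week 48".

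**Columns.** SAP 2.4.1 lists three safety groups for the entire period: Any Secukinumab 150 mg, "Any Secukinumab 300 mg" and Any Secukinumab. The efficacy list in the same section keeps a separate placebo-to-300 mg group, but the safety list does not.

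**Which column a switcher belongs to.**
- SAP 2.4.1: "For entire treatment period, the summaries by treatment group will be performed cumulatively by the actual treatment received", switchers included.
- SAP 2.1 allows a patient to appear in more than one group. It also says that the three groups defined there may serve for the entire period where appropriate.
- SAP 2.8 says that actual treatment departs from randomised treatment only when a patient was on the wrong treatment throughout the study. Taken at its word, this leaves switchers under placebo.

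SAP 2.4.1 starts the exposure clock of switched patients at the switch. No equivalent rule is given for laboratory values.

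**The concern.** In a patient randomised to 300 mg, the baseline comes just before the first 300 mg dose, and every later sample is on 300 mg. In a placebo switcher, the same baseline lies 16 weeks before the first active dose. A change in grade during those 16 weeks has nothing to do with secukinumab. Yet it sits between the reference value and the values read as treatment effects.

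Laboratory values are named in the trial's safety objective (protocol 2.2). Protocol 3.6 reports a small excess of mild neutropenia on secukinumab, and neutrophils are among the CTCAE-graded variables in SAP 2.8.3. The entire-period tables have no placebo column, so a reader of the Any 300 mg column cannot see how much of it arose before 300 mg was given. The same gap affects patients up-titrated from 150 mg: an abnormality that began on 150 mg can be scored under Any 300 mg.

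**Working it through.** The plan states no laboratory shift figure, so there is nothing to reproduce. The check reads the rules together and then gives an illustration.

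**Step 1: follow one placebo switcher through the rules.** Suppose the grade is 0 before the first placebo dose.

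| Course | Pre-first-dose baseline, only values on 300 mg | Pre-first-dose baseline, whole 52 weeks | Baseline just before first 300 mg dose, only values after it |
|---|---|---|---|
| Rises to grade 1 on placebo and stays there | 0 to 1, scored as a shift | 0 to 1, scored as a shift | 1 to 1, no shift |
| Rises to grade 1 on placebo, back to 0 before Week 16, stays 0 | 0 to 0, no shift | 0 to 1, scored as a shift | 0 to 0, no shift |
| Stays 0 on placebo, rises to grade 1 on 300 mg | 0 to 1, scored as a shift | 0 to 1, scored as a shift | 0 to 1, scored as a shift |

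The first row is misattributed under either window, because the reference value precedes placebo. The second row is misattributed only if the entire phase is taken literally as all 52 weeks for the Any 300 mg column.

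**Step 2: which tables are exposed.** The Day 1 to Week 16 table has a placebo column and no switch, so it is sound. The normal/low/high extreme-value table is built within one period: "Also the shifts to the most extreme laboratory test value within a Treatment Period will be presented as well". There only the fixed-baseline part applies, and only in Treatment Period 2. The entire-phase CTCAE shift tables carry both parts.

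**Step 3: size of the groups.** SAP section 3 plans 100, 100 and 50 patients.
- Any 300 mg with no up-titration: 100 + 50 = 150, of whom 50/150 = 33% are switchers.
- If 50 of the 150 mg patients are up-titrated (an assumption): 200, of whom 50/200 = 25% are switchers.
- Any Secukinumab: 100 + 100 + 50 = 250, of whom 50/250 = 20% are switchers.

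**Step 4: illustration.** Let q be the share of switchers whose grade for one parameter worsens on placebo. The documents give no value, so 2%, 5% and 10% are assumed. Misattributed patients = 50 × q, and points added = 100 × 50 × q / N.

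| q | Patients | Any 300 mg, N = 150 | Any 300 mg, N = 200 | Any Secukinumab, N = 250 |
|---|---|---|---|---|
| 2% | 1.0 | 0.7 | 0.5 | 0.4 |
| 5% | 2.5 | 1.7 | 1.3 | 1.0 |
| 10% | 5.0 | 3.3 | 2.5 | 2.0 |

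These are upper limits. Some placebo-period changes will resolve, and some of these patients would also worsen on 300 mg. If the 10% loss assumed in the sample size left 45 switchers, the first Any 300 mg column (N = 145) would read 0.6, 1.6 and 3.1 points. With a baseline before the first active dose and only later values counted, the contribution is 0.

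**Step 5: is the alternative baseline available?** Protocol 6.5 places blood draws before dosing, so a Week 16 sample is the last value on placebo. The hematology and chemistry row of protocol Table 6-1 appears to include Week 16. Column alignment is lost in the text version, so this should be confirmed against the original table.

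**The case against.** One pre-treatment baseline is conventional, simple and consistent with the SAP's general definition. Re-baselining gives patients in one column different reference points. The plan also offers other views: a separate Week 16 table with a placebo column, by-visit summaries and shifts, extreme values within a Treatment Period, and listings of patients with abnormal values. The exposed tables are descriptive, and neither the efficacy analysis nor the placebo-controlled safety comparison depends on them. All of this stands and limits the weight of the point. It does not remove the misattribution in the first row of the Step 1 table.

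The stronger objection is that the SAP never says placebo-period values enter Any 300 mg. Reporting by actual treatment received, with membership in more than one group, can fairly be read as keeping those values out. SAP 2.1 and 2.8 can even be read as leaving switchers under placebo, in which case events on 300 mg would appear as placebo events. This also stands. The SAP's text supports more than one allocation, and none of the readings comes with a stated observation window for laboratory values.

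A reader might go further and infer that over a third of the switchers' shifts are spurious. If two of about five post-baseline draws fall on placebo and each independently has a 5% chance of a grade increase, then 1 − 0.95^5 = 22.6% of switchers are scored as shifted, against 1 − 0.95^3 = 14.3% from draws on 300 mg. The gap is 37% of the shifts counted. The documents do not support that reading. The whole gap comes from admitting placebo-period draws to Any 300 mg, which the actual-treatment rule may exclude. Independent draws also allow nothing to persist, so the model does not measure the part of the problem that holds under either window.

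**Conclusion.** The concern holds for the entire-phase CTCAE shift tables. Wherever placebo switchers are shown under Any 300 mg or Any Secukinumab, an abnormality that began on placebo and persists past Week 16 is scored as a shift on active drug. This follows from the stated baseline and does not depend on how the window is read. Counting abnormalities that resolved before the switch is possible under the literal wording but not certain. The allocation of switchers to columns is itself contradictory across SAP 2.1, 2.4.1 and 2.8.

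The size cannot be derived from the documents. Under the assumed placebo worsening rates of 2% to 10%, the effect on a 150-patient Any 300 mg column is at most about 0.7 to 3.3 percentage points per parameter, and less if patients are up-titrated. Effects of that size could matter when an uncommon laboratory abnormality is described. The Week 16 tables are not affected. The correction should be made, but it concerns descriptive safety tables only.

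**What to change.** 1. Reconcile SAP 2.1, 2.4.1, 2.8 and 2.8.3 so that one rule states which column a switched patient's laboratory values belong to.
2. For the entire-period Any groups, count only laboratory values taken after the first dose of the treatment that defines the group. For Any 150 mg, close the window at the last sample before the first 300 mg dose.
3. Use as baseline the last value before that defining dose:
   - placebo switchers: the Week 16 pre-dose sample, identified by dosing date because the Week 16 analysis window in SAP 2.1.2 (Days 100 to 127) runs past the scheduled Day 113;
   - 150-to-300 mg patients in Any 300 mg: the last value before the first 300 mg dose;
   - 150 mg patients in Any 150 mg and in Any Secukinumab: the original baseline.
4. Keep the present rule for the Day 1 to Week 16 tables.

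The cost is SAP wording and programming. No new samples should be needed if Week 16 is scheduled as it appears to be. The small downside is that reference points will differ among patients pooled in one column, which calls for a table footnote.
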